5.2 Sequence of Procedures

A Schedule of Evaluations and Procedures is shown in Appendix 1.

5.2.1 Baseline/Pretreatment Period

The Investigator has the ultimate responsibility for obtaining written informed consent and HIPAA authorization. This process will be completed for a patient before performing any protocol-specific procedure. No sedation shall be administered to the patient within reasonable proximity, consistent with local IRB rules, to exert a meaningful pharmacologic effect before written informed consent and HIPAA authorization is obtained. Consent will include HIPAA authorization.

The following procedures must be performed prior to randomization (maximum timing prior to randomization in parenthesis):

- a. brief medical history (within 7 days)
- b. brief physical examination (within 7 days)
- c. vital signs (height, weight, body temperature, heart rate, systolic and diastolic blood pressure) (within 7 days)
- d. serum or urine pregnancy if of child bearing potential (within 7 days)
- e. serum creatinine (within 24 hours)
- f. PT-INR for patients receiving oral anticoagulation (warfarin derivatives) within 7 days prior to randomization (assessment must be done subsequent to last dose); if the last value prior to PCI (within 24 hours prior to randomization) is >1.3 times the control, patient is not eligible for enrollment (within 24 hours)
- g. hematology: hemoglobin, hematocrit and platelet count (within 24 hours)

The following baseline sampling will be performed immediately prior to PCI:

- a. Baseline blood sample for troponin
- b. Baseline blood sample for hemoglobin, hematocrit and platelet count
- c. ACT (see Appendix 4)

Whenever institutional policies allow, blood sampling can be obtained from sheaths, catheters, or central lines (including arterial lines) if available. Otherwise, an additional peripheral in-dwelling catheter may be inserted for venous blood sampling (e.g. heparin lock).

Blood pressure will be assessed per institutional policy.

5.2.2 Randomization

Once all baseline examinations and tests are completed, the site will once again carefully review the inclusion and exclusion criteria described in the protocol to ensure that the patient is eligible to enter the study.

Naming of oral P2Y₁₂ antagonist agent (clopidogrel, prasugrel, or ticagrelor) to be used post-randomization must be pre-specified prior to randomization.

Selection of either the femoral or radial access site must be pre-specified prior to randomization.

Randomization may occur only if all of the following criteria are satisfied:

- a. Consented patient is confirmed to be eligible for the study, AND
- b. name of intended oral P2Y₁₂ antagonist agent used post-randomization is pre-specified, AND
- c. access site for PCI is pre-specified, AND
- d. decision to proceed to PCI is finalized, AND
- e. timing between randomization and initiation of the PCI procedure is less than 2 hours.

Once the above criteria are satisfied, the patient may be randomized. The timing for randomization in this study is critical. The reason for timing the study drug administration so close to time of PCI is to minimize inappropriate patient enrollment. Situations where

this might occur include the procedure where PCI is aborted or otherwise not performed or when a decision is made not to administer study medication for whatever reason.

At randomization, the patient will be assigned a study number that will allow identification of the patient throughout the study, and the appropriate staff will prepare the corresponding study drug.

Patients will be randomized via a centralized randomization system to receive either tirofiban or eptifibatide.

The randomization will stratify patients according to femoral or radial access.

5.2.3 Timing of Oral Antiplatelet Therapy, PCI & Study Drug Administration

PCI will be performed according to institutional guidelines and standards. The index PCI procedure will be completed as clinically appropriate. Any PCI device approved by the FDA may be used (investigational stents may not be used in this study).

All clinical events from the time of study drug administration will be recorded. The number and position of coronary stents placed as well as the outcome of the procedure will be recorded.

All patients must receive aspirin (81 - 325 mg daily is recommended) and oral P2Y₁₂ antagonist therapy throughout the course of the study.

Patients who are on a P2Y₁₂ antagonist at time of randomization should remain on that same P2Y₁₂ agent post-randomization.

Patients who have not received any oral P2Y₁₂ antagonist therapy within 24 hours prior to randomization must receive a loading dose between randomization and 15 minutes after completion of the PCI (defined as final removal of the guiding catheter), preferably as close to time of randomization as possible.

Recommended loading doses for the oral P2Y₁₂ antagonist therapies are the following: clopidogrel 600 mg; prasugrel 60 mg; and ticagrelor 180 mg.

Patients will be administered unfractionated heparin as an initial I.V. bolus of 50 U/kg prior to PCI. Additional heparin boluses will be administered according to the suggested guidelines in Appendix 4.

Study drug will be prepared and labeled accordingly for each patient as described in the pharmacy manual. Tirofiban will be provided by Sponsor and packaged in 100 mL bags/vials containing 5.0 mg of tirofiban. Eptifibatide will be provided by the Institution and packaged in 10 mL bolus vials containing 20 mg eptifibatide and 100 mL infusion vials containing 75 mg of eptifibatide. See Pharmacy Manual for details of study drug preparation.

Patients assigned to short tirofiban will receive a 25 µg/kg bolus administered by I.V. push followed by a 0.15 µg/kg/min infusion for the duration of the PCI procedure plus a minimum of one hour and up to a maximum of two hours post-PCI. Sites have the option of administering the tirofiban 25 µg/kg bolus via I.V. pump over approximately 3 minutes or

bolus push with syringe. Sponsor will supply T-ports (Trudell Medical Marketing) to use for filling syringe for bolus administration.

Patients assigned to short tirofiban with renal insufficiency (creatinine clearance ≤ 60 mL/min) will receive a 25 $\mu\text{g}/\text{kg}$ bolus followed by a 0.075 $\mu\text{g}/\text{kg}/\text{min}$ maintenance infusion for the duration of the PCI procedure plus a minimum of one hour and up to a maximum of two hours post-PCI.

Patients assigned to eptifibatide will receive a 180 $\mu\text{g}/\text{kg}$ bolus followed by a 2.0 $\mu\text{g}/\text{kg}/\text{min}$ infusion for 18 hours post-PCI (minimum 12 hours mandated), with a second 180 $\mu\text{g}/\text{kg}$ bolus 10 min after the first.

Patients assigned to eptifibatide with renal insufficiency (creatinine clearance < 50 mL/min) will receive a 180 $\mu\text{g}/\text{kg}$ bolus followed by a 1.0 $\mu\text{g}/\text{kg}/\text{min}$ infusion for 18 hours post-PCI (minimum 12 hours mandated), with a second 180 $\mu\text{g}/\text{kg}$ bolus 10 min after the first.

Patients assigned to long tirofiban received a 25 $\mu\text{g}/\text{kg}$ bolus administered by I.V. push followed by a 0.15 $\mu\text{g}/\text{kg}/\text{min}$ infusion for 12-18 hours post-PCI.

Patients assigned to long tirofiban with renal insufficiency (creatinine clearance ≤ 60 mL/min) received a 25 $\mu\text{g}/\text{kg}$ bolus followed by a 0.075 $\mu\text{g}/\text{kg}/\text{min}$ maintenance infusion for 12-18 hours post-PCI.

The study drug boluses of tirofiban or eptifibatide will be administered intravenously by volume according to patient weight (see Appendix 3 for dosing tables). The bolus volume and infusion rate increases with increasing patient weight, but is capped at the patient weight of 153 kg and 121 kg for tirofiban and eptifibatide, respectively. Therefore, any patient randomized to tirofiban weighing over 153 kg will receive the same bolus volume and infusion rate as a patient randomized to tirofiban weighting 153 kg. Similarly, any patient randomized to eptifibatide weighing over 121 kg will receive the same bolus volume and infusion rate as a patient randomized to eptifibatide weighting 121 kg. Administration of the bolus will begin prior to the initiation of the PCI procedure. Initiation of the PCI procedure is defined as advancement of the guidewire out of the guiding catheter.

In patients with known coronary anatomy (i.e., a baseline angiogram was previously performed), the bolus will be administered after arterial access is achieved, prior to advancement of the guidewire out of the guiding catheter. In patients without a baseline angiogram, the bolus will be administered after completion of the initial angiography, once the decision has been made to proceed with PCI, prior to advancement of the guidewire out of the guiding catheter. The study drug infusion will be started immediately after completion of the bolus (first bolus in the case of eptifibatide). Upon completion of the study drug bolus administration and initiation of study drug infusion, advancement of the guidewire out of the guiding catheter and PCI may proceed.

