P2Y ₁₂ Receptor Antagonist:	As per local practice and physician discretion
Unfractionated Heparin:	50 U/kg bolus and repeat dosing guided per guidelines in Appendix 4
Short Tirofiban:	25 µg/kg bolus followed by a 0.15 µg/kg/min infusion for the duration of the PCI procedure plus a minimum of one hour and up to a maximum of two hours post-PCI
Eptifibatide:	180 µg/kg bolus followed by a 2.0 µg/kg/min infusion for 18 hours post-PCI (minimum 12 hours mandated), with a second 180 µg/kg bolus 10 min after the first
Long Tirofiban:	25 µg/kg bolus followed by a 0.15 µg/kg/min infusion for 18 hours post-PCI (minimum 12 hours mandated)

Tirofiban in premixed bags/vials (5 mg per 100 mL) to be supplied by sponsor.

Eptifibatide and all other medications to be supplied by hospital pharmacy.

EFFICACY MEASUREMENTS: The primary endpoint is a composite of events defined as any of the following within 48 hours following PCI or hospital discharge, whichever comes first: death, PPM (defined as ≥ 3 times the upper limit of normal troponin and at least 20% or greater than the baseline troponin value), uTVR or non-CABG-related major bleeding within 48 hours following PCI or hospital discharge, whichever comes first, quantified according to REPLACE-2 criteria.

SAFETY MEASUREMENTS: The primary safety endpoint will be non-CABG-related major bleeding within 48 hours following PCI or hospital discharge, whichever comes first, quantified according to REPLACE-2 criteria.

DATA ANALYSIS: All efficacy analyses will be performed on the modified intent-to-treat (MITT) population, i.e. all randomized patients who underwent PCI and received study drug. Safety analyses will be performed on the safety population, i.e. patients who received any study drug.

CONTACT INFORMATION

REPORTING OF SERIOUS ADVERSE EVENTS

ANY SERIOUS ADVERSE EVENT, WHICH REQUIRES EXPEDITED REPORTING, MUST BE REPORTED WITHIN 24 HOURS TO THE SPONSOR'S SAFETY SURVEILLANCE. See Protocol Section 8 (Adverse Events) for definitions (8.1), collection and reporting (8.4.2) of serious adverse events.

SAFETY SURVEILLANCE

[contact]

[contact]

MEDICAL MONITOR

[name], PhD

[contact]

Lead Clinical Research Organization

GVI Clinical Development Solutions Inc (GVI-CDS)

[name]

[name]

Contact Name: [name]

[contact]

[contact]

Academic Research Organization

Sarah Cannon Research Institute

[name]

[name]

[contact]

[contact]

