116-121	254-267	10.7 mL	7.0 mL/h	19.0 mL/h	3.5 mL/h	9.5 mL/h
>121	>267	11.3 mL	7.5 mL/h	20.0 mL/h	3.7 mL/h	10.0 mL/h

APPENDIX 4

ACT Measurements and Unfractionated Heparin Dosing Algorithm

For Patients Administered Background Unfractionated Heparin Therapy

In this study, the recommended target for the ACT is 200-300 seconds for patients administered background unfractionated heparin and randomized to either short or long tirofiban or eptifibatide. The following sequence of events is recommended for all patients administered background unfractionated heparin and randomized to either tirofiban or eptifibatide in this study:

If unfractionated heparin therapy was used pre-procedure, the infusion must be turned off before the start of the index procedure.

The following sequence of events is recommended for all patients administered background unfractionated heparin and randomized to either tirofiban or eptifibatide in this study:

- Establish vascular access.
- If the patient is not receiving intravenous unfractionated heparin, administer 50 U/kg of heparin and then proceed to the next step. If the patient has received an intravenous unfractionated heparin infusion within the previous 6 hours, proceed directly to the next step.
- Obtain ACT, perform guide shot angiograms.
- If ACT is ≥ 200 seconds, the intervention may begin.
- If ACT is < 200 seconds, administer additional heparin per the following dosing guidelines.

Baseline ACT (seconds)	Unfractionated Heparin dose (U/kg)
<150	40
150-174	25
175-199	10

- The initial bolus dose should not exceed 6,000 units.
- An ACT should be checked a minimum of 2 minutes after the initial unfractionated heparin bolus. If the ACT is ≥ 200 seconds, the intervention may begin.
- If the ACT is < 200 seconds, an additional bolus should be administered as in the table above. An ACT should then be checked a minimum of 2 minutes after this additional bolus.

- Additional boluses of unfractionated heparin may be given as in the table above until an ACT of ≥ 200 seconds is achieved.

These recommendations are to serve as guidelines. Additional boluses of unfractionated heparin may also be administered according to the discretion of the operator to achieve and maintain the ACT in the target range of 200-300 seconds.

During the procedure:

- After an initial ACT of 200-300 seconds is obtained, the ACT should be re-checked 30 minutes later, and every 30 minutes thereafter for the duration of the procedure.

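### Section 5.2.3 states the initial 50 U/kg heparin bolus without qualification, but Appendix 4 skips it after an intravenous heparin infusion in the previous 6 hours

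*Protocol*

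**What the plan says.** Protocol section 5.2.3 gives the heparin instruction in two sentences. The first is "Patients will be administered unfractionated heparin as an initial I.V. bolus of 50 U/kg prior to PCI". The second is "Additional heparin boluses will be administered according to the suggested guidelines in Appendix 4". No maximum and no exception for recent heparin is attached to the first dose, and the cross-reference covers only the doses after it.

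Appendix 4 sets out the first dose as a conditional step. One sentence reads "If the patient is not receiving intravenous unfractionated heparin, administer 50 U/kg of heparin and then proceed to the next step". The next reads "If the patient has received an intravenous unfractionated heparin infusion within the previous 6 hours, proceed directly to the next step"; that next step is to measure ACT. If ACT is at least 200 seconds, the intervention may begin. If it is lower, the operator is told to "administer additional heparin per the following dosing guidelines": 10 U/kg for ACT 175-199, 25 U/kg for 150-174 and 40 U/kg below 150. After the table comes "The initial bolus dose should not exceed 6,000 units".

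The synopsis entry for heparin is "50 U/kg bolus and repeat dosing guided per guidelines in Appendix 4". It can be read as placing both the bolus and the repeat doses under Appendix 4, or only the repeat doses.

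**The concern.** A patient who comes to PCI shortly after a heparin infusion falls under two different instructions for the first dose. Section 5.2.3 is worded as an instruction and describes Appendix 4 as suggested guidance, so a site that notices the difference has a textual reason to follow section 5.2.3.

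What is at stake is bleeding risk for the individual patient. The heparin is given with a high-dose GPIIb/IIIa inhibitor, and a bolus already given cannot be withdrawn when a later ACT reads high. Appendix 4's own rule during the procedure is to give no more heparin once ACT is 200 seconds or above, so an unconditional first bolus runs against the protocol's own dosing logic.

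**Working it through.** **Can these patients be enrolled?** Yes. Section 4.2 excludes low-molecular-weight heparin and bivalirudin within 12 hours before randomization, but not unfractionated heparin. Appendix 4 foresees a pre-procedure heparin infusion and requires it to be turned off before the index procedure.

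**First-dose difference after a recent infusion.** Inputs: 50 U/kg from section 5.2.3 and the ACT-table doses from Appendix 4. The weights are assumptions, because the documents give no weight distribution. Formula: (50 − table dose) × weight.

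| ACT (seconds) | Appendix 4 first dose (U/kg) | Difference (U/kg) | 60 kg | 85 kg | 120 kg |
|---|---|---|---|---|---|
| at least 200 | 0 | 50 − 0 = 50 | 3,000 U | 4,250 U | 6,000 U |
| 175-199 | 10 | 50 − 10 = 40 | 2,400 U | 3,400 U | 4,800 U |
| 150-174 | 25 | 50 − 25 = 25 | 1,500 U | 2,125 U | 3,000 U |
| below 150 | 40 | 50 − 40 = 10 | 600 U | 850 U | 1,200 U |

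These are differences in the first dose, not in total heparin. Below 200 seconds, repeat ACT-guided boluses may narrow them. At 200 seconds or above, Appendix 4 calls for no bolus before the intervention begins.

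**The 6,000-unit line.** Its target can be read in two ways.

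- *It caps the 50 U/kg step.* It then binds above 6,000 / 50 = 120 kg. In support, section 5.2.3 uses the word initial for the 50 U/kg dose, and Appendix 4 introduces the table doses as additional heparin.
- *It caps the first table dose.* At the largest table dose it binds above 6,000 / 40 = 150 kg. In support, the line follows a table headed by baseline ACT. The next bullet checks ACT after the initial bolus, although ACT was already obtained after the 50 U/kg step, and then sends the operator back to the same table for a further bolus.

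At 153 kg (the top band of the tirofiban dosing table, used only as a reference weight) section 5.2.3 gives 50 × 153 = 7,650 U. On the first reading that is 7,650 − 6,000 = 1,650 U above the limit. On the second reading the 50 U/kg step is not limited, so the excess is 0. The range is therefore 0 to 1,650 U, depending only on what the line means.

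**The case against.** The strongest reply is that section 5.2.3 summarises and Appendix 4 is the algorithm. Giving the standard dose in the body and its conditions in an appendix is ordinary protocol structure. Sites are pointed to Appendix 4 by section 5.2.3, by the synopsis and, for the pre-PCI ACT, by section 5.2.1. Section 5.2.3 also says that all patients must receive aspirin, but does not use the word all for heparin. These points stand as mitigation: the protective content exists and is signposted, so error is less likely. They do not resolve the conflict, because section 5.2.3 refers only the additional boluses to Appendix 4.

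A second reply is that a patient whose infusion has just been stopped is no longer receiving heparin, so Appendix 4's first condition also gives 50 U/kg and the two sections agree. The overlap is real. But on that reading the 6-hour look-back has almost no function, since only a patient with an infusion still running would skip the bolus. The specific sentence more naturally governs, and if the overlap is genuine, Appendix 4 itself needs rewording.

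A third reply is that first-dose figures say little about total exposure. That is fair, particularly for heavy patients. Appendix 4 limits one bolus and not the total: even on the reading that caps the 50 U/kg step, at 153 kg with ACT 150-174 it allows 6,000 + 25 × 153 = 9,825 U, more than the 7,650 U first dose in section 5.2.3.

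A reader might also infer that section 5.2.3 clearly breaches a 6,000-unit maximum for everyone above 120 kg. The documents do not support that, because the line may cap the table dose instead. Nor does the synopsis add a second firm conflict, since its wording can be read either way.

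**Conclusion.** The conflict over the recent-infusion exception holds and should be corrected. Its size is 10 to 50 U/kg in the first dose, depending on ACT. The clearest case is a patient already at 200 seconds or above, who gets 50 U/kg under one section and none under the other. This rests on the 6-hour sentence governing when the two conditions in Appendix 4 overlap; the unit figures also rest on the assumed weights.

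The 6,000-unit line is an ambiguity for the sponsor to settle, not an established conflict.

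Because major bleeding is the primary safety endpoint and part of the primary composite, a reader might infer that this biases the comparison. The documents do not support that: heparin is background therapy and the wording is the same in every arm. Sample size, power and analysis are unaffected. The number of patients involved and the effect on bleeding cannot be derived from the documents. A patient of 120 kg or less with no recent heparin infusion gets the same first dose under both sections.

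**What to change.** In section 5.2.3, write: *initial bolus of 50 U/kg, subject to the recent-infusion exception and maximum in Appendix 4; omit if an intravenous unfractionated heparin infusion was given within the previous 6 hours, and dose by ACT*. Use matching wording in the synopsis for clarity.

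In Appendix 4, change the first condition to *has not received an intravenous unfractionated heparin infusion within the previous 6 hours*, which removes the overlap. Confirm which step the 6,000-unit limit applies to and place it beside that step. If it is the 50 U/kg step, repeat the limit in section 5.2.3.

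The cost is a few wording changes, or a memo to sites. No new data, visits or patients are needed. The protocol describes enrolment as continuing in two arms, so the correction would still reach patients.

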5.2.4 In The Event of Thrombotic Complications

At the end of the PCI procedure all patients will be assessed to determine if a thrombotic complication persists according to the following criteria:

1. abrupt or threatened closure, with reduced flow, and/or
2. no reflow or slow flow, due to distal embolization, and/or

3. visible thrombus.

Determination of whether one or more of these criteria has been satisfied will be at the determination of the investigator.

Patients administered short tirofiban experiencing a thrombotic complication will continue to receive an infusion of tirofiban at a dose of 0.15 µg/kg/min (or 0.075 µg/kg/min for patients with renal insufficiency (creatinine clearance ≤60 mL/min)) for a minimum of 12 hours following PCI. See Appendix 3 for dosing tables.

Patients administered eptifibatide experiencing a thrombotic complication will continue to receive an infusion of eptifibatide at a dose of 2.0 µg/kg/min (or 1.0 µg/kg/min for patients with renal insufficiency (creatinine clearance <50 mL/min)) for 18 hours following PCI (minimum 12 hours mandated, no maximum infusion duration). See Appendix 3 for dosing tables.

Patients administered long tirofiban experiencing a thrombotic complication continued to receive an infusion of tirofiban at a dose of 0.15 µg/kg/min (or 0.075 µg/kg/min for patients with renal insufficiency (creatinine clearance ≤60 mL/min)) for 18 hours following PCI (minimum 12 hours mandated, no maximum infusion duration). See Appendix 3 for dosing tables.

5.2.5 Following the Procedure

Short tirofiban will be infused for the duration of the procedure plus a minimum of one hour and up to a maximum of two hours post-PCI. For example, if the procedure takes 25 minutes (i.e. 25 minutes from the time of advancement of the guidewire out of the guiding catheter to final removal of the guiding catheter) then tirofiban will be infused for a total of 25 minutes plus a minimum of one hour (for a total infusion time of 85 minutes) and up to a maximum of two hours (for a total infusion time of 145 minutes). For another example, if the PCI procedure takes 55 minutes, then tirofiban will be infused for a total of 55 minutes plus a minimum of one hour (for a total infusion time of 115 minutes) and up to a maximum of two hours (for a total infusion time of 175 minutes).

Eptifibatide will be infused for a total of 18 hours following PCI (minimum 12 hours mandated).

Long tirofiban was infused for a total of 18 hours following PCI (minimum 12 hours mandated).

During study drug administration and following discontinuation of study drug, the patient will be observed for signs of bleeding. Blood pressure and heart rate will be monitored according to the institution's standard procedures.

For the definition of procedure duration, final removal of the guiding catheter will define procedure completion.

